16.5 OTHER STATISTICAL CONSIDERATIONS AND DATA ANALYSIS

Effects of gender, age and race

The individual effects, if any, of gender, age, and race on the primary treatment effects will be determined where numbers permit. No attempt will be made to determine the effect of two or more of these variables acting together.

Additional summaries and analyses

A summary will be prepared to show dropouts/retention over time in each treatment group and for major subgroups. The number of missing observations will be compared between treatments and for major subgroups. The compliance of each group at each assessment day will be summarized. Unusual blood level determinations (e.g., indicating lack of compliance) will be presented.

16.6 SAMPLE SIZE ESTIMATE

The proposed primary outcome measure is the weekly proportion of cocaine non-use days. Power analyses were made based on assumptions of normal distribution, equal correlation between observations at any two times (exchangeable) working correlation and a common standard deviation of 33.5%. These assumptions are based on preliminary results of an eightweek selegiline study (Protocol Number: CS-1017), in which an oral dose of selegiline was compared to placebo in cocaine dependent subjects. We further make the assumption that a 10% increase in the proportion of cocaine non-use days of the STS treatment group over the placebo group would be considered clinically significant. Based on the sample size calculation for GEE procedures proposed by Liu and Liang²⁰, then 110 subjects will be required in each arm to detect this clinically meaningful difference with a power of 80% at the 0.05 level of significance. The retention rates in studies of cocaine addicts currently being conducted by NIDA are approximately 70%, therefore at least 150 subjects should be randomized into each treatment to ensure an adequate sample size at the end of the trial.

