16.4 ANALYSIS PLAN

Each of the primary and secondary efficacy outcome measures will be analyzed for the intent-totreat and for the evaluable population. Major differences in the results, if any, will be further explored. While there is every intent to be complete in describing the analyses to be performed, it is not possible to anticipate every contingency and some adjustments may be required to meet constraints posed by the structure of the data.

All statistical tests will be two-sided at a 5% level of alpha. Confidence intervals will be two-sided with a 95% confidence coefficient.

Primary Efficacy Outcome

The primary outcome variable for each subject is the weekly proportion of cocaine non-use days. Each subject's weekly proportion is equal to the number of his/her cocaine non-use days divided by the number of his/her non-missing study days during that week (a maximum of 6 days for week 1 and 7 days for weeks 2 through 8).

The weekly mean proportion of cocaine non-use days on study will be compared between treatment groups using Generalized Estimating Equations (GEE). GEE provide a model-based regression methodology applicable for the analysis of the correlated data that will result from this repeated measures longitudinal study.

The GEE procedure proposed by Liang and Zeger¹⁸ and Zeger and Liang¹⁹ (Biometrics, 1986) model the population average and has several useful features:

- 1. It can be used to analyze different types of outcomes such as continuous, binary, or count.
- 2. It can be used to analyze an unbalanced design caused by either differing numbers of observations per person or by observations taken at different times.
- *3.* The parameter estimates are consistent even if assumptions about the variance structure are not completely accurate.

Secondary Efficacy Outcomes

As a secondary analysis, the baseline proportion of cocaine non-use days, site, gender, diagnosis of ADD, severity of depression during screening, and their first-order interactions with treatment will also be included in the model. Presentation will include the full model with all terms and a reduced model containing only significant terms.

Unless the primary response analysis implies the need for a more elaborate model, between group comparisons of the secondary outcomes will be performed as follows:

- 1. Proportion of successful subjects, measures A, B, and C, will be assessed by Chi-square tests.

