16.8 INTERIM ANALYSIS

A single interim analysis will be performed after one half of the subjects have completed the study. The Pampallona-Tsiatis²¹ group sequential design for two-sided hypothesis will be used. The Pampallona-Tsiatis design will allow the possibility of early stopping a trial whenever a large treatment difference is observed or small treatment difference is observed. Using the Pampallona-Tsiatis Design and O'Brien-Fleming²² boundary method, the interim analysis will be performed at a nominal level of α =0.006 and β =0.07 while the final analysis will be performed at α =0.044 and β =0.13. This ensures an overall significance level of 0.05 and power of 0.8.

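### At the stated 70% retention, 150 per arm gives 105 completers, not the 110 required, and no sample-size allowance is stated for the interim look, so the stated calculation does not support the 80% power claim

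*Protocol*

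**What the plan says.** Section 16.6 (Sample Size Estimate) assumes "a common standard deviation of 33.5" per cent and "equal correlation between observations at any two times (exchangeable) working correlation". It takes as its target that a "10% increase in the proportion of cocaine non-use days of the STS treatment group over the placebo group would be considered clinically significant". From a cited GEE sample-size method it concludes that "110 subjects will be required in each arm to detect this clinically meaningful difference with a power of 80% at the 0.05 level of significance". It then puts retention at approximately 70% and reasons: "therefore at least 150 subjects should be randomized into each treatment to ensure an adequate sample size at the end of the trial". The value of the correlation is not given, and the interim analysis is not mentioned.

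Section 16.4 (Analysis Plan) sets the level: "All statistical tests will be two-sided at a 5% level of alpha".

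Section 16.8 (Interim Analysis) plans one look when half the subjects have completed, using a Pampallona-Tsiatis design that can stop for a large or a small difference. Alpha is given as 0.006 at the interim and 0.044 at the end, and beta as 0.07 and 0.13. The section closes: "This ensures an overall significance level of 0.05 and power of 0.8". It does not tie that statement to 110 or to 150.

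**The concern.** There are two gaps between what section 16.6 computes and what the protocol claims.

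- **Retention.** The argument runs from 110 required, through 70% retained, to 150 randomised, so as to have enough subjects when the trial ends. That is a completer argument, and its arithmetic does not close.
- **Interim look.** The 110 is presented as an ordinary 80% power, 5% level calculation. Stopping for futility at an interim look costs power unless the maximum sample size is raised. Splitting alpha and beta between two looks yields power of 0.8 only if that increase is made, and none is stated.

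A null result would be read against the 80% figure, and 150 per arm is the basis for the trial's size in the synopsis and section 9. Both should follow from a calculation that a reader can check.

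**Working it through.** **Inputs.** From section 16.6: SD 33.5; difference 10, read as percentage points; power 0.80; 110 required, 150 randomised, retention 0.70. From section 16.4: two-sided alpha 0.05 and eight weekly proportions. From section 16.8: one look at half the information; alpha 0.006/0.044; beta 0.07/0.13. The correlation rho is not stated and has to be back-solved.

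**1. The 110.** For a single measurement, n = 2 × (1.960 + 0.842)² × 33.5² / 10² = 176.2 per arm. With eight exchangeable measurements this is multiplied by (1 + 7·rho)/8. Setting 176.2 × (1 + 7·rho)/8 = 110 gives rho = 0.571. So 110 can be matched by choosing rho, but not reproduced independently: rho = 0.5 would give 99 and rho = 0.7 would give 130.

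**2. The 150.**
- 150 × 0.70 = 105, five short of 110.
- 110 / 0.70 = 157.1, so 158 per arm (316 in total).
- The common shortcut 110 × 1.30 = 143 does not give 150 either.
- 110 / 150 = 0.733, so 150 suffices only at 73.3% retention.

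**3. Power with 105 completers, no interim look.** Φ(2.802 × √(105/110) − 1.960) = Φ(0.777) = 78.1%, against 80.0% with 110.

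**4. Adding the interim look.** I integrated the two-stage design numerically at information 0.5 under two readings of section 16.8:
- (a) the stated alpha and beta figures taken as amounts spent at each look: reject at |Z1| > 2.748, stop for futility at |Z1| < 0.581, final critical value 1.947;
- (b) a Pampallona-Tsiatis boundary of O'Brien-Fleming shape: 2.736, 0.698 and 1.935.

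Both keep overall alpha at 0.050.

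| | (a) stated split | (b) O'Brien-Fleming shape |
|---|---|---|
| Inflation needed for 80% power | 1.043 | 1.058 |
| Completers per arm, 110 × inflation | 114.7, so 115 | 116.4, so 117 |
| Randomised per arm at 70% retention | 164 | 167 |
| Power with 110 completers | 78.4% | 77.8% |
| Power with 105 completers | 76.5% | 75.9% |

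The difference detectable with 80% power at 105 completers is 10 × √(110/105) = 10.2 points without the interim look, and 10 × √(114.7/105) to 10 × √(116.4/105), about 10.5 points, with it.

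**5. All randomised subjects in the GEE.** Under the exchangeable model a subject with m observed weeks carries information proportional to m/(1 + (m − 1)·rho). At rho = 0.571 this is 1 for one week and 8/4.995 = 1.602 for eight, so one week is worth 1/1.602 = 62% of a completer.
- At 70% retention there are 45 dropouts per arm. If each gives one week, effective n = 105 + 45 × 0.624 = 133. Power is 86.9% fixed and 84.9% to 85.4% with the interim look.
- If each gives four weeks, effective n = 146. Power is 89.8% fixed and 88.0% to 88.5% with the interim look.
- To get back to 80%, one week is needed from 5/28.1 = 18% of dropouts with no interim look, and from about 35% (a) to 41% (b) with it.

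**The case against.** The strongest case for the plan is that completers are not the analysis set. The intent-to-treat population in section 16.3 is everyone randomised. Section 16.4 takes each weekly proportion over non-missing days and chooses GEE partly because it accepts unequal numbers of observations. Section 13.6 keeps subjects who stop the patch but stay in psychosocial treatment on the full assessment schedule. Step 5 shows what this is worth. In addition, 70% is given as approximate and 150 as a minimum.

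Most of this stands. A reader might infer that 80% power is not delivered, or that 75% to 76% is the trial's real power. The documents support neither: those figures hold only if dropouts contribute nothing, which is not the planned analysis. What the objection does not do is repair section 16.6. That section does not argue from partial data; it discounts for retention to secure a final count and gets the count wrong. The favourable figures in step 5 also assume that dropout is uninformative and that the treatment effect is not diluted.

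Two other strong readings should be resisted.
- A reader might take 0.044 as the final p-value cut-off, which with the futility rule would give 74.8% at 105 completers. But the stated levels add exactly to 0.05 and 0.20, which fits a split of the two error rates. As literal cut-offs they would give overall alpha of 0.044 with the futility rule enforced, or 0.047 without it, not the 0.05 claimed.
- A reader might say that 110 certainly omits the inflation. Because rho is not reported, this cannot be proved. If the factor were already inside 110, the fixed-sample n would be about 104 to 105 and rho about 0.53 to 0.54, which is no less plausible. The fair statement is that no allowance is stated.

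**Conclusion.** The point holds as an error in the stated calculation, not as proof of an underpowered trial. On section 16.6's own figures 150 randomised per arm leaves 105, not 110, and 158 would be needed. Section 16.8 asserts power of 0.8 with no stated inflation for a design that needs a factor of about 1.04 to 1.06.

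On the completer logic of section 16.6 the retention slip costs 1.9 points of power and the interim look a further 1.6 to 2.2 points. These figures rest on reading the target as 10 percentage points, on treating 110 as a fixed-sample number (hence rho = 0.571), and on the interim look falling at half the information.

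For the analysis actually planned, 150 per arm probably reaches 80% or more, subject to the conditions in step 5. I rate the severity as minor to moderate: the arithmetic error is certain, its effect is modest even on the least favourable reading, and it does not require a larger trial.

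**What to change.** Keep 300 subjects and make three changes.

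1. In section 16.6, correct the retention sentence: 150 per arm at 70% retention gives 105 completers, with about 76% power for 10 points on completers alone under the sequential plan. Label this as a completers-only figure; it should not stand as the power of the primary analysis.
2. In the same section, restate power for all randomised subjects under the planned GEE, giving the assumed correlation, the expected retention pattern and the group-sequential inflation, and say whether 110 already includes that inflation.
3. In section 16.8, replace the assurance of 0.8 power with the result of that calculation.

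The cost is one reworded paragraph and one aligned sentence, with no extra subjects. The stated power may become slightly less favourable.

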16.7 ADAPTIVE RANDOMIZATION PROCEDURE

Adaptive random allocation of subjects to study groups was developed to balance groups with respect to screening prognostic variables. The procedure allocates treatment assignment based on the assignments and prognostic variable levels for all previously enrolled subjects. The treatment groups will be balanced with respect to gender, diagnosis of ADD, historical self-report of cocaine use for the last 30 days at the time that informed consent is given (balanced for

 \geq 18 days of use and < 18 days of use), and severity of depression determined by HAM-D score (balanced for scores \geq 11 and <11). A new subject will be randomized with a "biased coin" procedure which uses randomization probabilities, favoring the treatment with the deficit enrollment, to improve the balance on group assignment (Efron¹⁰). The randomization process will be performed by computer at CSPCC.

16.8 INTERIM ANALYSIS

A single interim analysis will be performed after one half of the subjects have completed the study. The Pampallona-Tsiatis²¹ group sequential design for two-sided hypothesis will be used. The Pampallona-Tsiatis design will allow the possibility of early stopping a trial whenever a large treatment difference is observed or small treatment difference is observed. Using the Pampallona-Tsiatis Design and O'Brien-Fleming²² boundary method, the interim analysis will be performed at a nominal level of α =0.006 and β =0.07 while the final analysis will be performed at α =0.044 and β =0.13. This ensures an overall significance level of 0.05 and power of 0.8.

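### Section 16.8 states the final test level as 0.044, which is the error spent at that look and not a p-value cut-off, and it conflicts with the blanket 5% in 16.4

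*Protocol*

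**What the plan says.** Section 16.4 opens the analysis plan with a general rule: "All statistical tests will be two-sided at a 5% level of alpha". It stands just above the primary efficacy analysis, makes no exception for it and does not refer to 16.8. Section 16.6 sizes the trial at the 0.05 level with 80% power.

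Section 16.8 adds a group sequential rule: "A single interim analysis will be performed after one half of the subjects have completed the study". The design is the two-sided Pampallona-Tsiatis design with O'Brien-Fleming boundaries, which permits "early stopping a trial whenever a large treatment difference is observed or small treatment difference is observed". For the first look it says "the interim analysis will be performed at a nominal level of α =0.006 and β =0.07". The rule for the last look, together with the claim made for the whole design, reads "while the final analysis will be performed at α =0.044 and β =0.13. This ensures an overall significance level of 0.05 and power of 0.8". The section does not say that these figures are amounts of error spent.

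**The concern.** The protocol gives two levels for the same final test. A final p-value of 0.047 succeeds under 16.4 and fails under 16.8, and nothing says which section governs.

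The 0.044 in 16.8 also looks like the wrong kind of number. Error spent at successive looks adds up to the overall level. Nominal p-value cut-offs do not, because the interim and final statistics are correlated. Since 0.006 + 0.044 is exactly 0.05 and 0.07 + 0.13 is exactly 0.20, the figures behave as error spent, yet the text says the final analysis is performed at 0.044. An analyst who compares the final p-value with 0.044 would not be running the named design. At stake is the threshold for declaring the trial positive, and whether the stated 0.05 and 0.8 describe the test as carried out.

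**Working it through.** **Inputs.** Two looks, the interim at half the information (16.8, taking half of the subjects as half the information); alpha 0.006 and 0.044, beta 0.07 and 0.13, overall 0.05 and power 0.8 (16.8); two-sided 5% (16.4).

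**Step 1: the plan's own figure.** 0.006 + 0.044 = 0.050 and 0.07 + 0.13 = 0.20. Read as error spent, the stated 0.05 and 0.8 reproduce exactly.

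**Step 2: solve the named design.** Let Z1 and Z2 be the interim and final statistics, with correlation √0.5 = 0.707 and drift θ at the final look. With O'Brien-Fleming shape:

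- final critical value C1
- interim efficacy bound C1/√0.5
- interim futility bound (inner wedge) θ√0.5 − C2/√0.5, with θ = C1 + C2

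Solving for overall alpha 0.05 and power 0.8 gives C1 = 1.935, C2 = 0.948 and θ = 2.882. The interim efficacy bound is 1.935 × 1.414 = 2.736. The wedge is 2.882 × 0.707 − 0.948 × 1.414 = 0.70. Hence:

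- alpha spent at the interim is 0.0062, which is also the nominal p there because it is the first look
- alpha spent at the final look is 0.0438
- the nominal p at the final look is 2 × [1 − Φ(1.935)] = 0.053
- beta spent is 0.087 and 0.113

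Rounded, 0.0062 and 0.0438 are the protocol's 0.006 and 0.044. The final cut-off is 0.053. The beta split does not match the stated 0.07 and 0.13, so a second wedge was solved to spend exactly 0.006/0.044 and 0.07/0.13. It gives a futility bound of |Z1| < 0.58, a final critical value of 1.947 (p = 0.0515) and θ = 2.861.

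**Step 3: overall alpha when a p-value cut-off is used.** Overall alpha = P(|Z1| > c1) + P(w ≤ |Z1| ≤ c1 and |Z2| > c2) under the null. Here c1 = 2.748 (p = 0.006), c2 is the final cut-off, and w is the futility bound (0 if non-binding).

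| Final cut-off | Non-binding | Binding, wedge 0.58 | Binding, wedge 0.70 |
|---|---|---|---|
| p < 0.044 (Z 2.014) | 0.0465 | 0.0436 | 0.0426 |
| p < 0.05 (Z 1.960) | 0.0524 | 0.0487 | 0.0474 |
| Cut-off giving 0.05 | p 0.0476 (Z 1.981) | p 0.0515 (Z 1.947) | p about 0.053 (Z about 1.935) |

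A simulation of 4 million trials gave 0.0467, 0.0437 and 0.0526 for the p < 0.044 non-binding, p < 0.044 binding (wedge 0.58) and p < 0.05 non-binding cells.

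**Step 4: power.** With the same formula at the design drift and the stop followed, a final cut-off of 0.044 gives power 0.785 (wedge 0.58) or 0.783 (wedge 0.70), against the stated 0.80.

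**Step 5: how often the two sections disagree.** Under the null, the chance of a final p between 0.044 and 0.05 is 0.0524 − 0.0465 = 0.0059 if futility is non-binding, and 0.0487 − 0.0436 = 0.0051 with the 0.58 wedge.

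**The case against.** The strongest defence is that nothing is miscalculated. As error spent, 0.006 and 0.044 give the overall 0.05 that 16.8 claims, and the word nominal is attached only to the interim look, where nominal and spent alpha coincide. The 5% in 16.4 can be taken as the general or overall level, with 16.8 as the specific rule that divides it. Exact critical values and the status of the futility stop are often left to a statistical analysis plan. The match to the named design is also only partial, because the beta split differs.

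Much of this stands. The point concerns labelling and consistency, not a wrong sum, and "error spent" is an inference from the exact sums and the alpha match. The lack of a critical value is not itself a fault.

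Two things remain. No text ranks 16.4 against 16.8 or calls the 5% an overall level. And even if 16.8 governs, 0.044 is still not the final cut-off of the design it names.

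A reader might infer more: that neither level can deliver 0.05, or that the plan inflates the type I error. The documents do not support that. The error-spent reading delivers 0.05; 0.044 as a cut-off is conservative; and a cut-off of 0.05 exceeds the overall level only if the futility stop is treated as non-binding, whereas 16.8 names a design in which that stop is part of the boundary.

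**Conclusion.** The concern holds as a fault of wording and consistency. The final level in 16.8 is an amount of error spent written as a test level, and it conflicts with 16.4.

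The numerical effect is small. Applied as a p-value cut-off, 0.044 gives an overall alpha of about 0.043 to 0.047 and costs about 1.5 points of power. A cut-off of 0.05 gives 0.047 to 0.049 with the stop binding, and 0.0524 without it, an excess of 0.0024. The two sections would disagree in about 0.5% to 0.6% of trials under the null.

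The results assume normally distributed statistics and an interim at exactly half the information. Severity is minor to moderate: no data or subjects are affected, but a success threshold should not be open to choice once the p-value is known.

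**What to change.** Before the interim analysis:

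- In 16.8, label 0.006/0.044 and 0.07/0.13 as error spent at each look, and give the final critical value of the design actually used. With the futility stop binding, as the named design has it, this is about |Z| > 1.935 (p about 0.053) for the standard wedge, or |Z| > 1.947 (p about 0.0515) for a wedge that spends the stated beta of 0.07. Say which wedge applies. These values depend on the stop being followed: if it is overridden, a final cut-off of 0.0515 gives an overall alpha of 0.0538.
- If the sponsor prefers non-binding futility, use |Z| > 1.981 (p < 0.0476). That departs from the named design, and power should then be restated at about 0.79 if the stop is followed.
- In 16.4, except the primary test from the blanket 5% and refer to 16.8.

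The cost is two or three sentences, with no change to data collection or enrolment.

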17 DATA MANAGEMENT AND CASE REPORT FORMS (CRF)

Data management activities and statistical analytical support will be coordinated through the Department of Veterans Affairs Cooperative Studies Program Coordinating Center in [name] (CSPCC). Data will be collected at the study sites on CRFs, which will be supplied by CSPCC. Completed forms will be submitted on a regular basis to CSPCC.

When data are received at the CSPCC, they will be verified and edited prior to being entered into the main study database. Incomplete or inaccurate data will be returned to the sites for correction using a series of edit reports that are specifically tailored for the study. Sites will resolve data inconsistencies and errors prior to returning data to the CSPCC. All corrections and changes to the data will be reviewed prior to being entered into the main study database. NIDA/DTR&D and the participating sites will receive reports at least monthly regarding the quality and quantity of data submitted to the CSPCC.

Site investigators agree to routine data audits by the staff of the VACSP monitoring unit, as well as by NIDA or Somerset Pharmaceuticals. VACSP monitors will routinely visit each site to assure that data submitted on the appropriate forms are in agreement with source documents at the sites. They will also verify that study medications have been properly stored and accounted for, subject informed consent for study participation has been obtained and documented in the patient's progress notes, all essential documents required by Good Clinical Practice regulations are on file, and sites are conducting the study according to the research protocol. Any inconsistencies will be resolved, and any changes to the data forms will be made using established CSPCC procedures.

The CSPCC will also prepare summary reports of the data so that progress of the study can be monitored. Various reports will be prepared for NIDA, Somerset Pharmaceuticals and the Data Safety and Monitoring Board, and others, as appropriate. These reports, as well as the final analyses, will be prepared in cooperation with the coordinating center in Perry Point.

